6.2. Safety and tolerability outcomes

- 1. Change in weight from baseline
- 2. The incidence of all-cause mortality will be summarised.
- All adverse events will be coded using the Medical Dictionary for Regulatory Activities (MedDRA) and will be presented by Preferred Term within each MedDRA System Organ Class (SOC).
- 4. Treatment emergent adverse events (TEAEs) are adverse events (AEs) which started or worsened on or after the first administration of BPaMZ up to and including 14 days after the last study drug administration. In the case where it is not possible to define an AE as treatment-emergent or not, the AE will be classified as treatment-emergent.
 - a. The incidence of the following events will be summarised for further medical analysis:
 - i. Incidence of TEAEs;
 - ii. Incidence of TEAEs by Severity;

- iii. Incidence of TEAEs by DMID toxicity grade;
- iv. Incidence of Drug-Related TEAEs;
- v. Incidence of Serious TEAEs;
- vi. Incidence of TEAEs Leading to Early Withdrawal;
- vii. Incidence of TEAEs leading to Death.
- 5. Quantitative and qualitative clinical safety laboratory measurements (newly notable grade 3 or 4 laboratory parameters according to DMID grading), including observed and change from baseline.
- 6. Electrocardiogram (ECG) results (heart rate, RR interval, PR interval, QRS interval, QT interval and QTc interval, including observed QT/QTc intervals and change from baseline) will be categorised.
- 7. Results of any paternity outcome during or after treatment with pretomanid at early withdrawal and week 78 follow-up will be tabulated.

7. Definitions and Data Handling Issues

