### Safety and Tolerability:

- Change in weight from baseline.
- Incidence of Treatment Emergent Adverse Events (TEAEs) presented by incidence, severity, drug relatedness, seriousness, leading to early withdrawal, and leading to death.
- Quantitative and qualitative clinical safety laboratory measurements, including observed and change from baseline. Quantitative and qualitative electrocardiogram (ECG) results (heart rate, RR interval, PR interval, QRS interval, QT interval and QTc interval, including observed QT/QTc intervals and change from baseline) will be categorized.

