## **10 Statistical Analysis**

The statistical analysis plan (SAP), which will contain details of the analyses specified in this section, will be written, and signed off prior to first patient randomized.

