## 10.5 Safety and Tolerability Analysis

- The incidence of all-cause mortality will be summarized.
- All adverse events will be coded using the Medical Dictionary for Regulatory Activities (MedDRA) and will be presented by Preferred Term within each MedDRA System Organ Class (SOC).
- Treatment-emergent adverse events (TEAEs) are defined as AEs which started at or after the first administration of IMP and includes those events started prior to the first administration of IMP but which worsened after the first intake. Adverse events starting after the last administration of IMP until the last scheduled visit/assessment/measurement will be regarded as treatment emergent.
- The incidence of the following events will be summarized for further medical analysis:
  - Incidence of TEAEs;
  - Incidence of TEAEs by Severity;
  - Incidence of TEAEs by DMID toxicity grade;
  - Incidence of Drug-Related TEAEs;
  - Incidence of Serious TEAEs;
  - Incidence of TEAEs Leading to Early Withdrawal;
  - Incidence of TEAEs leading to Death.

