1.0 / 15 Feb 2021	Initial version	
1.1 / 20 Dec 2022	Updates made to outcome analysis and circulated for comment	
1.2 / 30 Jan 2023	Updates made to Statistical analysis and circulated for further comments	
1.3/ 06 Feb 2023	Updates made to outcome sections to align more with the protocol Additional analysis details added	
1.4/ 02 Mar 2023	Updates made post expert review	
1.5/ 14 Mar 2023	Further updates made after expert review	
1.6/ 17 April 2023	Updates made to section on pharmacokinetics	

1. Introduction

This document outlines the statistical analysis for the BPaMZ/SEM trial, Protocol Version 4.0, dated 07 April 2022.

Pretomanid is being used in an antimicrobial combination regimen(s) to treat patients with pulmonary tuberculosis. The primary purpose of this trial "BPaMZ/SEM" is to evaluate the potential effect of pretomanid on human testicular function whilst being used in a 26-week antimicrobial combination regimen consisting of bedaquiline (B) plus pretomanid (Pa) plus moxifloxacin (M) and pyrazinamide (Z) (BPaMZ).

All participants will receive the same regimen of BPaMZ once daily for 26 weeks.

The participant population will be patients with drug resistant TB (DR-TB) defined as Mycobacterium tuberculosis (MTB) that is sensitive to fluoroquinolones but

- 1. Mono-resistant to rifampicin or isoniazid, OR
- 2. Resistant to both rifampicin and isoniazid (MDR-TB)

2. Objectives

The primary objective is to assess the male reproductive safety of pretomanid in the regimen (BPaMZ) of bedaquiline 200mg (200mg daily for 8 weeks then 100 mg daily for 18 weeks), together with pretomanid 200 mg (1x daily) + moxifloxacin 400 mg (1x daily) + pyrazinamide 1500 mg (1 x daily) for 26 weeks in participants with Drug-resistant (DR) pulmonary TB.

The secondary objective is to evaluate the efficacy, safety and tolerability after 26 weeks of active treatment for TB and follow up for 52 weeks after start of the above described treatment regimen in participants with Drug-resistant (DR) pulmonary TB.

3. Sample Size

A total of 20 evaluable male participants diagnosed with DR-TB who completed the trial will be required.

Twenty-five participants (25) will be enrolled in the trial assuming a 20% participant dropout of the trial. If the dropout rate is higher than 20% before finishing 26 weeks of treatment, the enrolment of additional participants may be considered to assure that 20 complete.

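### SAP 6.2 ends the treatment-emergent window 14 days after the last dose, protocol 10.5 runs it to the last scheduled visit, and the SAP does not declare the difference

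*SAP*

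**What the plan says.** Protocol 10.5 is explicit about the period after treatment: "Adverse events starting after the last administration of IMP until the last scheduled visit/assessment/measurement will be regarded as treatment emergent". For events already present before dosing, its definition "includes those events started prior to the first administration of IMP but which worsened after the first intake", with no end date attached to the worsening.

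SAP 6.2 item 4 counts an AE as treatment emergent if it starts or worsens from the first dose of BPaMZ "up to and including 14 days after the last study drug administration". It adds a fallback: "In the case where it is not possible to define an AE as treatment-emergent or not, the AE will be classified as treatment-emergent".

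Both sections then list the same seven summaries: all TEAEs, by severity, by DMID grade, drug-related, serious, leading to early withdrawal, and leading to death. They serve one endpoint. Protocol 4.3 lists TEAE incidence "presented by incidence, severity, drug relatedness, seriousness, leading to early withdrawal, and leading to death".

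The SAP introduction ties the two documents together: "This document outlines the statistical analysis for the BPaMZ/SEM trial, Protocol Version 4.0, dated 07 April 2022". Protocol Section 10 describes the SAP as the document "which will contain details of the analyses specified in this section". Nowhere does the SAP say that it departs from protocol 10.5 or give a reason.

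Outside the TEAE tables, SAP 6.2 codes and presents all AEs by system organ class and preferred term, and item 2 reads: "The incidence of all-cause mortality will be summarised".

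**The concern.** The tables keep the same names, but a different set of events enters them. An analyst who follows the SAP and a reader who relies on the protocol could arrive at different numbers for the same endpoint. Nothing in either document would tell them why.

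The protocol collects AEs through Week 78 (9.2), and its synopsis makes safety over the 52 weeks after treatment part of the secondary objective. SAP 7.6 schedules safety data in the Week 44 analysis and all data in the final one. Yet for an on-schedule completer the SAP's TEAE window closes at Week 28. Apart from events that cannot be classified, later AEs add nothing to the TEAE tables at either analysis.

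What is lost is the breakdown. A late AE with a known onset date would appear as a coded term, but no planned summary would show its severity, DMID grade, relatedness or seriousness, or whether it led to early withdrawal. With about 25 participants, one serious or drug-related late event would visibly change a table.

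**Working it through.** **Inputs**
- Treatment length: 26 weeks (SAP 7.5; protocol 7.1).
- Follow-up: Week 26 to Week 78 (protocol 5.2), stated as 52 weeks after the end of therapy (protocol synopsis; SAP 6.1).
- SAP window after the last dose: 14 days (SAP 6.2 item 4).
- Protocol window after the last dose: to the last scheduled visit (protocol 10.5), which is Week 78.
- Follow-up visit window: ±14 days (SAP 7.5).

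**Step 1. Reproduce the plan's follow-up length.** 78 − 26 = 52 weeks, or 52 × 7 = 364 days. This matches the stated 52 weeks. Protocol 3.2 and SAP 2 count the 52 weeks from the start of the regimen instead, but that does not move the visit schedule or AE collection from Week 78.

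**Step 2. Follow-up time counted under the protocol only.** On-schedule completer: last dose at Week 26; SAP window closes at Week 26 + 2 = 28; protocol window closes at Week 78. Difference: 364 − 14 = 350 days = 50 weeks. Share: 350/364 = 96.2%.

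**Step 3. Share of the whole window.** SAP: 26 × 7 + 14 = 196 days. Protocol: 78 × 7 = 546 days. 196/546 = 35.9%.

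**Step 4. Sensitivity to the visit window.**
- Last visit 14 days early: (350 − 14)/(364 − 14) = 336/350, or 48 of 50 weeks, 96.0%.
- Last visit 14 days late: (350 + 14)/(364 + 14) = 364/378, or 52 of 54 weeks, 96.3%.

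**Step 5. One event under both rules.** Take an AE with a known onset at Week 35. It starts (35 − 26) × 7 = 63 days after the last dose. Since 63 > 14, it is not a TEAE under the SAP. Since Week 35 precedes Week 78, it is a TEAE under the protocol. The SAP fallback does not help, because the status of this event can be determined. The same split applies to a pre-treatment condition that first worsens at Week 35.

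**Step 6. What could fall in the gap.** The flow chart schedules no safety laboratory tests at Weeks 35 to 78 and one ECG, at Week 44, so few routine laboratory AEs are likely. Reproductive hormones are still drawn at Weeks 35, 44, 52, 65 and 78 (footnote g), and a laboratory change that the investigator judges clinically significant is an AE (protocol 9.2.2). A late hormone-related AE is therefore possible. The documents give no AE rate, so a count of affected events cannot be derived.

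**The case against.** The case for leaving this alone has some force.

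- **A short window can be a sound choice.** Some participants may start re-treatment before Week 78 (protocol 1.1.1, footnote b), and withdrawn participants with confirmed positive cultures or symptomatic TB are referred for other therapy (protocol 6.3.4). Under the protocol window, events arising on that other therapy would count as emergent on BPaMZ. This stands as a downside of the wider window. It does not excuse an undeclared departure.
- **Little depends on it.** TEAEs are an other-secondary endpoint in a single-arm trial analysed descriptively. No test or primary conclusion uses this window. This also stands.
- **Late events are reported anyway.** Partly true. The all-AE presentation and the mortality summary keep them, causality is recorded for each AE (protocol 9.1.3), and serious AEs are still reported within 24 hours (protocol 9.2). Late hormone values are summarised under SAP 5 item 4 whatever their AE label. The breakdowns are still missing.
- **A sentence and a listing would do.** That would cure the silence in the SAP, but protocol 10.5 would still define the same tables differently.

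Four stronger readings are tempting, and the documents do not support them. A reader might take 96% as the share of events lost; it is calendar time. A reader might infer that late safety data go uncollected or unreported; they do not. A reader might infer that the departure was deliberate because the SAP names Protocol Version 4.0. Version 1.0 of the SAP is dated 15 Feb 2021, before that protocol, and nothing shows how the clause arose. Finally, a reader might apply the figure to the 56-day halt in SAP 7.3, but protocol 7.3 withdraws a participant who reaches 56 missed doses, so that is not a completer case.

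**Conclusion.** The two current texts conflict on which events are treatment emergent, and nothing else in the documents reconciles them. For an on-schedule completer the disagreement covers Weeks 28 to 78: 50 of 52 follow-up weeks, 96% of follow-up time (96.0% to 96.3% across the visit window). The figure assumes a last dose at Week 26 and a last visit at Week 78. It does not describe early withdrawals, for whom only serious AEs are collected afterwards.

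The effect is confined to descriptive safety tables. Semen, hormone and paternity summaries, AE collection and SAE reporting do not change. The number of affected events is unknown and may be small. The documents do not show that the 14-day window is wrong in itself; the defect is that it replaces the protocol's definition without saying so. It should be settled before database lock, so that the definition is not chosen with the late events in view.

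**What to change.** Before database lock:

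1. Align SAP 6.2 item 4 with protocol 10.5.
2. Show the seven existing TEAE summaries by period of onset or worsening: first dose to 14 days after the last dose; later, to the last scheduled visit. This keeps the 14-day view.
3. Footnote that after early withdrawal the later period contains serious AEs only.
4. Flag late events that start after re-treatment with other TB therapy.

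The cost is a short SAP edit, a period column in existing tables and one flag. AE data are already collected through Week 78. The downsides are a little more tabulation, possibly higher TEAE counts, and some later events that arise on other TB therapy, which the split and the flag keep visible.

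If the sponsor prefers 14 days as the main definition, the SAP should state the departure and tabulate later AEs with the same breakdown, and protocol 10.5 should be amended. That route costs more, because protocol Section 15 requires agreement by the investigator, ethics committee and sponsor, and approval before implementation.

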Hypoglycemia	55-64 mg/dL	40-54 mg/dL	30-39 mg/dL	<30 mg/dL or abnormal glucose with mental status changes or coma	
Hyperglycemia (non-fasting and no prior diabetes)	116 - 160 mg/dL	161- 250 mg/dL	251 - 500 mg/dL	> 500 mg/dL or abnormal glucose with ketoacidosis or seizures	
Hypocalcemia (corrected for albumin)	8.4 - 7.8 mg/dL	7.7 - 7.0 mg/dL	6.9 - 6.1 mg/dL	< 6.1 mg/dL or abnormal calcium with life threatening arrhythmia or tetany	
Hypercalcemia (correct for albumin)	10.6 - 11.5 mg/dL	11.6 - 12.5 mg/dL	12.6 - 13.5 mg/dL	> 13.5 mg/dL or abnormal calcium with life threatening arrhythmia	
Hypomagnesemia	1.4 - 1.2 mEq/L	1.1 - 0.9 mEq/L	0.8 - 0.6 mEq/L	< 0.6 mEq/L or abnormal magnesium with life- threatening arrhythmia	
Hypophosphatemia	2.0 - 2.4 mg/dL	1.5 -1.9 mg/dL or replacement Rx required	1.0 -1.4 mg/dL intensive therapy or hospitalization required	< 1.0 mg/dL or abnormal phosphate with life- threatening arrhythmia	
Hyperbilirubinemia (when accompanied by any increase in other liver function test)	1.1 - <1.25 x ULN	1.25 - <1.5 x ULN	1.5 – 1.75 x ULN	> 1.75 x ULN	
Hyperbilirubinemia (when other liver function is in the normal range)	1.1 - <1.5 x ULN	1.5 - <2.0 x ULN	2.0 – 3.0 x ULN	> 3.0 x ULN	
BUN	1.25 - 2.5 x ULN	2.6 - 5 x ULN	5.1 - 10 x ULN	> 10 x ULN	
Hyperuricemia (uric acid)	7.5 – 10.0 mg/dL	10.1 – 12.0 mg/dL	12.1 – 15.0 mg/dL	>15.0 mg/dL	
Creatinine	1.1 - 1.5 x ULN	1.6 - 3.0 x ULN	3.1 - 6 x ULN	> 6 x ULN or dialysis required	

ENZYMES					
	Grade 1	Grade 2	Grade 3	Grade 4	
AST (SGOT)	1.1 - <2.0 x ULN	2.0 – <3.0 x ULN	3.0 – 8.0 x ULN	> 8 x ULN	
ALT (SGPT)	1.1 - <2.0 x ULN	2.0 – <3.0 x ULN	3.0 – 8.0 x ULN	> 8 x ULN	
GGT	1.1 - <2.0 x ULN	2.0 – <3.0 x ULN	3.0 – 8.0 x ULN	> 8 x ULN	
Alkaline Phosphatase	1.1 - <2.0 x ULN	2.0 – <3.0 x ULN	3.0 – 8.0 x ULN	> 8 x ULN	
Amylase	1.1 - 1.5 x ULN	1.6 - 2.0 x ULN	2.1 - 5.0 x ULN	> 5.1 x ULN	
Lipase	1.1 - 1.5 x ULN	1.6 - 2.0 x ULN	2.1 - 5.0 x ULN	> 5.1 x ULN	

URINALYSIS				
	Grade 1	Grade 2	Grade 3	Grade 4
Proteinuria	1+ or 200 mg - 1 gm loss/day	2-3+ or 1- 2 gm loss/day	4+ or 2-3.5 gm loss/day	nephrotic syndrome or > 3.5 gm loss/day
Hematuria	microscopic only <10 rbc/hpf	gross, no clots >10 rbc/hpf	gross, with or without clots, OR red blood cell casts	obstructive or required transfusion

CARDIOVASCULAR					
	Grade 1	Grade 2	Grade 3	Grade 4	

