7.7. Newly notable abnormalities

A newly notable laboratory abnormality is defined as an abnormality observed post baseline that meets the notable criteria shown in Table 1 below and that did not exist at baseline. Participants can still meet the criteria for newly notable laboratory event if the baseline value is missing.

Lab Test Type	Laboratory Variable	SI Units		
Liver	AST	$>$ 3 x ULN and \leq 5 x ULN		
		> 5 x ULN and ≤ 8 x ULN		
		> 8 x ULN		
	ALT	$>$ 3 x ULN and \leq 5 x ULN		
		> 5 x ULN and \leq 8 x ULN		
		> 8 x ULN		
	Total Bilirubin	> 2 x ULN		
	Alkaline Phosphatase (ALP)	> 2 x ULN		
Chemistry Labs	Other:			
	ALT or AST > 3 x ULN and total bilirubin > 2 x ULN			
	ALT or AST > 3 x ULN and total bilirubin > 2 x ULN and ALP <2 x			
	ULN (potential Hy's law case)			
	Lipase	> 2 x ULN to \leq 5 x ULN		
		> 5 x ULN		

Table 1: Notable Criteria for Laboratory Data

8. Analysis Populations and Definitions

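### SAP Table 1 does not count the DMID grade 3 or 4 laboratory results that SAP 6.2 promises, and its baseline rule conflicts with SAP 7.6

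*SAP*

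**What the plan says.** SAP 6.2 item 5 makes clinical laboratory measurements a safety outcome. It specifies "newly notable grade 3 or 4 laboratory parameters according to DMID grading" and adds that these are reported "including observed and change from baseline". It does not restrict the analytes.

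SAP 7.7 gives the working definition. A newly notable abnormality is a post-baseline one "that meets the notable criteria shown in Table 1 below and that did not exist at baseline". Table 1 has rows for AST, ALT, total bilirubin, ALP, two combined liver criteria and lipase. The bilirubin row is "Total Bilirubin > 2 x ULN", with no condition on other liver tests. The ALP row is "Alkaline Phosphatase (ALP) > 2 x ULN".

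Protocol Appendix 2 holds the DMID table. It grades bilirubin on two scales. The row headed "Hyperbilirubinemia (when accompanied by any increase in other liver function test" has as its grade 3 and grade 4 cells "1.5 – 1.75 x ULN > 1.75 x ULN". The other row, for normal liver function, puts grade 3 at 2.0 to 3.0 × ULN and grade 4 above 3.0. ALP is grade 2 from 2.0 to below 3.0, grade 3 from 3.0 to 8.0 and grade 4 above 8. Appendix 2 also grades haematology, electrolytes, uric acid and creatinine, all of which Protocol 8.3 collects.

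SAP 7.6 has its own rule for safety summaries. An abnormality is included if the criterion was not met at baseline, or if its toxicity grade is higher than at baseline. The highest grade within a visit is summarised and all values are listed.

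**The concern.** The outcome and its working definition describe different sets of results. A programmer following 6.2 would count DMID grades 3 and 4 for every graded test. A programmer following 7.7 would count five tests on other cut-offs. A programmer following 7.6 would use a different baseline rule. The reported number of men with a newly notable result depends on which section is followed.

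The affected tests are relevant to this regimen. Protocol 2.2.1.4 reports that a trial of pretomanid, moxifloxacin and pyrazinamide was put on partial clinical hold because of deaths associated with hepatotoxicity. Protocol 2.2.2.3 says hyperuricaemia is common with pyrazinamide, yet uric acid has no row. Protocol 6.2 excludes haemoglobin below 8.0 g/dL, so a man can enter at 8.0, and DMID grade 3 starts at 7.9; haemoglobin has no row either.

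**Working it through.** There is no planning figure to reproduce. The check sets each Table 1 cut-off (SAP 7.7) against the DMID grade 3 and 4 limits (Protocol Appendix 2), in multiples of ULN from 1 to 10 in steps of 0.01.

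**Step 1: cut-offs.**

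| Test | DMID grade 3 or 4 starts | Table 1 starts | Grade 3/4 not meeting the row | Below grade 3 but counted |
|---|---|---|---|---|
| Bilirubin, another liver test raised | 1.5 | >2 | 1.5 to 2.0 (grade 3 to 1.75, grade 4 above 1.75 to 2.0) | none |
| Bilirubin, other liver tests normal | 2.0 | >2 | exactly 2.0 only | none |
| ALP | 3.0 | >2 | none | above 2.0 to <3.0 (grade 2) |
| AST, ALT | 3.0 | >3 | exactly 3.0 only | none |
| Lipase | above 2 | >2 | none | none |

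Lipase grades use the limits in Protocol 9.3.2. The exact-boundary cases are a matter of inequality signs and of no practical weight. The substantive mismatches are the first bilirubin row and ALP.

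**Step 2: what the bilirubin gap means for one man.** With ALT 3.5 × ULN and bilirubin 1.9 × ULN, bilirubin is DMID grade 4 (1.9 > 1.75) but fails the bilirubin row (1.9 < 2) and the combined rows. He is still flagged on the ALT row (3.5 lies above 3 and at or below 5). If instead the raised ALT is at or below 3 × ULN and no other row is met, nothing flags him.

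**Step 3: coverage.** Blood tests that are both collected (Protocol 8.3) and graded (Appendix 2) are, by my count: haemoglobin, neutrophils, platelets, white cells, sodium, potassium, glucose, calcium, magnesium, phosphate, bilirubin, urea, uric acid, creatinine, AST, ALT, ALP and lipase. That is 18. Table 1 has 5 of them: 5/18 = 28%. The other 18 − 5 = 13 have no row, so no grade 3 or 4 result in them can be newly notable.

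**Step 4: baseline rule.** Protocol 6.2 excludes ALP at or above 3.0 × ULN but allows 2.0 to <3.0 after discussion and approval. Take a man at 2.5 × ULN at baseline who rises to grade 3 (3.0 or more).
- SAP 7.7: he already met the >2 row at baseline, so the abnormality existed then and he is not newly notable.
- SAP 7.6: grade 3 is higher than his baseline grade 2, so he is included.

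The ALP row therefore misses no grade 3 or 4 value by its cut-off, but it can miss one through the baseline rule.

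**Step 5: weight of one case.** With 25 men enrolled, one omitted participant is 1/25 = 4 percentage points of the reported incidence.

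**The case against.** The strongest reply is that these results are not lost. SAP 7.6 provides highest-grade summaries, a grade-above-baseline rule and listings, and none of this is tied to Table 1. SAP 6.2 also promises observed values and change from baseline. SAP 9.2 gives the range, so an extreme haemoglobin or potassium would show. TEAEs are tabulated by DMID grade.

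This stands in part. A reader might infer that severe bilirubin rises and all blood-count and electrolyte toxicity go unreported. The documents do not support that: every bilirubin rise above 2 × ULN meets the row, and the other outputs exist. But they do not replace the promised count:
- SAP 7.6 names no analytes and defines no grade 3 or 4 count.
- Continuous summaries carry no grades, and the shift tables in SAP 9.2 use the reference range.
- Under Protocol 9.2.2 a laboratory change becomes an adverse event only if the investigator judges it clinically significant. Protocol 9.3 names grade 3 and 4 abnormalities separately from clinically significant ones, so the two sets differ.

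A reader might also infer that patient monitoring is weakened, particularly with two QT-prolonging drugs. That does not follow. Protocol 9.3 asks for confirmation of grade 3 or 4 results within 48 hours where possible, Protocol 9.3.4 has electrolytes checked when QTcF reaches 500 msec, and ECG is a separate outcome. The mismatch affects tabulation, not detection.

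Nor do the documents call Table 1 the main laboratory safety table. It is one element of a descriptive, single-arm analysis. Counting ALP from above 2 × ULN is cautious in itself; the fault is presenting it as grade 3 or 4.

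Finally, the text could be reconciled more cheaply by declaring Table 1 a supplementary liver and lipase list. That would remove the contradiction, but would leave no defined grade 3 or 4 count for the other 13 tests.

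**Conclusion.** The plan is wrong as written, within limits. The rule in SAP 7.7 does not produce the outcome in SAP 6.2 item 5. It leaves out DMID grade 3 and 4 bilirubin between 1.5 and 2.0 × ULN when another liver test is raised, counts grade 2 ALP, and has no row for 13 of 18 collected and graded tests. SAP 7.6 and 7.7 also disagree on how baseline is treated.

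The effect is confined to the newly notable tabulation. How many men it would change cannot be known from the documents.

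The conclusion rests on three assumptions. Table 1 is complete as read from the PDF; its row-group labels look displaced, so it should be checked against the original. Appendix 2 is the DMID table that SAP 6.2 means. And an abnormality existed at baseline when the same Table 1 row was already met then.

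**What to change.** In SAP 7.7, define a newly notable laboratory abnormality as any post-baseline DMID grade 3 or 4 result (Protocol Appendix 2) whose grade is higher than at baseline. This brings 7.7 into line with 7.6. Apply it to every analyte that is both collected and DMID-graded, and name those analytes. Use both bilirubin scales, and say which tests count as another raised liver test.

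Keep the AST and ALT bands, the lipase rows and the combined liver rows, including the potential Hy's law row. Label the bilirubin and ALP rows above 2 × ULN as additional criteria outside DMID grading.

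The cost is SAP wording and longer safety tables. No new data are needed.

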## No protocol waivers will be granted by the TB Alliance

## 6.1 Inclusion Criteria

Participants are required to meet all the following inclusion criteria during the screening period to be enrolled. Patients must abstain from ejaculation for at least 2 days prior to screening clinic visit.

1. Understands study procedures and voluntarily provides written informed consent prior to the start of any study-specific procedures.

- 2. Male gender 18 years or over.
- 3. Body weight (in light clothing and no shoes)  $\ge$  45kg.
- 4. A positive molecular test for tuberculosis in sputum either at screening or within one month prior to enrollment.
- 5. Disease Characteristics:
  - Participants must have been diagnosed with TB prior to or at screening.
  - Participants' TB should be resistant to rifampicin and/or isoniazid (historical evidence of resistance to rifampicin and/or isoniazid is acceptable within 3 months prior to screening), and susceptible to fluoroquinolones by rapid sputum-based tests
  - Participants who have had previous treatment for DR-TB for more than 3 months at start of screening should be discussed with the medical monitor.
- 6. A chest x-ray, within 6 months prior to or at the screening visit, which in the opinion of the Investigator is compatible with pulmonary TB.
- 7. Participants will be required to use a double contraceptive method during the whole treatment duration and 18 weeks post dose.
- 8. Can comply with the protocol and the assessments therein, including all restrictions.

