#### Paternity Questionnaire:

This questionnaire is aimed at collecting additional data on male reproduction after treatment completion of this regimen containing pretomanid. The questionnaire at week 78 or early withdrawal. Will include a general question whether the participant has fathered any children during or after treatment with the pretomanid-containing regimen

If yes, the number of children and the month and year of their birth will be obtained. A completed questionnaire will be entered into the database for all participants. Data will be analyzed descriptively based on the data collected in this trial.

Data collected may be added to the ongoing paternity survey of male reproduction which is currently being collected from previous and ongoing TB Alliance trials with pretomanid containing regimens (i.e., STAND, Nix-TB, SimpliciTB and ZeNix). See Appendix 5 for the questionnaire questions.

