## **Appendix 5: Paternity Questionnaire**

## **Paternity Questionnaire**

Please answer the following questions:

Did you father a child(ren) after your start of the trial?

Yes 🗆	No 🗆
-------	------

If yes, how many? \_\_\_\_\_

- What month and year was/were your child(ren) born? (Add more lines if necessary)
  - Child 1: MMM/YYYY
  - Child 2: MMM/YYYY
  - Child 3: MMM/YYYY

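### The paternity table has no step from birth to conception, so children conceived before the first dose can be counted as paternity on or after pretomanid

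*SAP*

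**What the plan says.** The SAP lists paternity as the last safety and tolerability outcome (6.2 item 7): "Results of any paternity outcome during or after treatment with pretomanid at early withdrawal and week 78 follow-up will be tabulated". It gives no further definition or derivation.

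The data come from the questionnaire in Protocol Appendix 5, scheduled in the flow chart at Week 78 and at early withdrawal. Its opening question is "Did you father a child(ren) after your start of the trial". After the number of children, the only other item is "What month and year was/were your child(ren) born".

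Protocol 9.4 describes the same form differently. There the question is "whether the participant has fathered any children during or after treatment with the pretomanid-containing regimen", followed by: "If yes, the number of children and the month and year of their birth will be obtained". Its purpose is stated as: "This questionnaire is aimed at collecting additional data on male reproduction after treatment completion of this regimen containing pretomanid". On analysis it says: "Data will be analyzed descriptively based on the data collected in this trial". It adds that the data may be joined to a wider paternity survey covering other pretomanid trials. Footnote o of the flow chart (Section 1.1.1) uses a third time frame, namely during and after the trial.

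Inclusion criterion 7 (Protocol 6.1) reads: "Participants will be required to use a double contraceptive method during the whole treatment duration and 18 weeks post dose".

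**The concern.** Only conception can say something about testicular function under the drug. A birth dates from a conception many months earlier. A man whose partner was already pregnant at Day 1 may become a father during treatment or follow-up, yet that child carries no information about pretomanid.

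The form is anchored to the start of the trial and records no conception date, gestational age or term status. The SAP labels the result as paternity on or after treatment. *Father* is not defined as conceiving or as having a child born. No rule excludes or separates pre-dose conceptions.

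At stake is a small table that could read as reassurance about fertility on the regimen when some or all of its entries predate the drug. If the data are added to the wider survey without a conception rule, the same label could go with them.

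**Working it through.** **Plan's own figures.** The documents give no expected number of births or conception rate, so there is no paternity figure to reproduce. The timeline does reproduce: 26 weeks of treatment + 52 weeks of follow-up = Week 78, and 26 + 18 = Week 44 for the end of required contraception.

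**Inputs**
- Treatment: 26 weeks (Protocol 7.1; SAP 7.5).
- Last questionnaire: Week 78 (Protocol 1.1.1).
- Contraception: to Week 44 (Protocol 6.1 item 7).
- Sperm production cycle of around 75 days plus about 10 days of transit (Protocol 2.1, Trial Design Rationale).
- Assumption, not in the documents: g = 38 weeks from conception to birth, range 34 to 40.

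**Formula.** Conception week = birth week − g, with Day 1 as week 0.

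**1. Which births predate the drug.** Conception falls before Day 1 when birth week < g. That means births before Week 38 (Week 34 to Week 40 over the range).

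**2. Worked births**

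| Birth week | Conception week, g = 38 | Range, g = 40 to 34 | Reading |
|---|---|---|---|
| 26 | −12 | −14 to −8 | Before Day 1 |
| 36 | −2 | −4 to +2 | Uncertain |
| 50 | 12 | 10 to 16 | After Day 1, but see step 5 |
| 58 | 20 | 18 to 24 | On treatment |

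Nothing in the plan distinguishes these four children.

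**3. Early withdrawal.** A birth reported at a withdrawal within the 26 treatment weeks occurred no later than Week 26. The latest possible conception is 26 − 34 = Week −8. Over the whole assumed range, every such birth is a pre-dose conception.

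**4. Effect of contraception.** The earliest conception the protocol permits is at Week 44. Its birth week is 44 + 38 = 82 (44 + 34 = 78 to 44 + 40 = 84). That is at or after the last questionnaire. A Week 78 visit at the late end of its 14-day window would reach Week 80, and so would catch only births at 36 weeks or less after conception (44 + 36 = 80). If contraception is used as required and works, nearly every birth on the form was therefore conceived before Day 1. The rest would be contraceptive failures, non-use, or an early birth conceived just after Week 44. Conversely, the latest conception a Week 78 form can see at g = 38 is 78 − 38 = Week 40, still inside the contraception period.

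**5. Day 1 is not a clean boundary either.** 75 + 10 = 85 days, and 85/7 = 12.1 weeks. A conception in roughly the first 12 weeks draws on sperm whose production began before dosing. The birth at Week 50 (conceived at Week 12, or day 84) is on treatment by date but is not clear evidence of sperm production under the drug.

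**The case against.** The strongest case on the other side has four parts.

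**The question can be read correctly.** *Father* can mean conceive, and both Protocol 9.4 and SAP 6.2 limit the item to treatment or afterwards. Birth month is a follow-up detail, not the test for inclusion. This stands in part. Pre-dose conceptions can be counted, but not every man will report them. A reader might infer that every positive answer is wrongly tabulated; the documents do not show that. They show an undefined term, differing time frames and no rule.

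**The data allow repair.** Birth month is collected, so each child could be placed against dosing by hand. True, and this is why the remedy is cheap. But the SAP plans no such step, and a table under its present label would not reveal the problem.

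**The size is unknown.** A reader might take 38/78 = 49% (34/78 = 44% to 40/78 = 51%) as the share of births conceived before the drug. Those are shares of calendar time, not of children. Turning them into shares of births needs conception rates before and during the trial, and the documents give none. This objection stands in full.

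**The item is minor.** Paternity is a descriptive safety item in about 25 men, with no test, threshold or decision rule. The trial's question is answered by sperm count, the other semen outcomes and hormones. This also stands, and it limits the point to the paternity table. Pooling is stated only as a possibility, and the survey's own classification rules are not in the documents.

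**Conclusion.** The concern holds in a limited form. As written, the plan allows children conceived before the first dose to be tabulated as paternity on or after pretomanid. Assuming 34 to 40 weeks from conception to birth, this applies to births up to about Week 38 (34 to 40) and to any birth reported at a withdrawal within the 26 treatment weeks. Because contraception runs to Week 44, most births recorded in compliant men would be of this kind.

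No percentage of births can be stated. The result rests on the assumed interval, which a very preterm birth would break, and on contraception being used and effective.

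A reader might go further and conclude that the trial's finding on testicular function is compromised. The documents do not support that: the primary endpoint is change in total sperm count and does not use the questionnaire. The fault is a label that errs toward reassurance on a secondary descriptive item. It is worth correcting before the Week 78 analysis and before any pooling.

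**What to change.** In SAP 6.2 item 7:

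- Derive an estimated conception month for each child as birth month minus about 38 weeks, with a stated range such as 34 to 40.
- Tabulate children in four groups: conceived before Day 1; from Day 1 to last dose; after last dose; and uncertain, where the range spans a boundary. For the uncertain group, say which boundary.
- Count only the on-treatment and after-treatment groups as paternity during or after treatment.
- Flag conceptions within about 85 days of Day 1 as drawing on sperm whose production began before dosing.

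Align the time frame in flow-chart footnote o, Protocol 9.4, Appendix 5 and SAP 6.2, and say whether *father* means conception or birth. Carry the same split into any data added to the wider survey.

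The SAP part costs one derivation and a few table columns, using birth months and dosing dates already recorded. Aligning the form and the protocol text needs a wording amendment. The downside is that the interval is assumed and birth is dated only to the month. A 6-week range (40 − 34) plus up to about 4 weeks within the month gives a conception window of about 10 weeks, so some children will stay in the uncertain group. In a trial this small, that may be a noticeable part of a short list.
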